1.1 BACKGROUND					
2. STUDY OBJECTIVES		6			
3. STUDY DESIGN		6			
3.1 STUDY OUTCOME MEA	ASURES	6			
4. PARTICIPANT ENTR	Υ	7			
4.1 PARTICIPANT RECRUIT 4.2 PRE-REGISTRATION EV	MENT ALUATIONS	7 7			
4.3 INCLUSION CRITERIA		8			
4.4 EXCLUSION CRITERIA		8			
4.5 WITHDRAWAL CRITER	IA	8			
5. ADVERSE EVENTS		8			
5.1 DEFINITIONS		8			
5.2 REPORTING PROCEDUI	RES	9			
6. ASSESSMENT AND	FOLLOW-UP	9-10			
7. STATISTICS AND DA	ATA ANALYSIS	11			
8. REGULATORY ISSU	ES	11			
8.1 ETHICS APPROVAL		11			
8.2 CONSENT		12			
8.3 CONFIDENTIALITY		12			
8.4 INDEMNITY		12			
8.5 SPONSOR		12			
8.6 FUNDING		12			
8.7 AUDITS AND INSPECTI	ONS	12			
9. STUDY MANAGEM	ENT	12			
10. PUBLICATION POLI	сү	12			
11. REFERENCES		14			
APPENDIX 1: Summary of i APPENDIX 2: Sub-studies	nvestigations and assessments	15 16			

STUDY SUMMARY

TITLE: Bariatric surgery vs. Medical care for obesity and polycystic ovarian syndrome related infertility: The BAMBINI randomised-controlled clinical trial

DESIGN: Open-label randomised controlled trial

AIMS: To investigate the safety and efficacy of obesity surgery vs. standard medical care for women with PCOS, obesity and oligo or amenorrhea.

OUTCOME MEASURES: Number of ovulatory cycles within the 12 month follow-up period.

POPULATION: Women with polycystic ovarian syndrome and obesity

ELIGIBILITY: Pre-menopausal women \ge 18 years old, Body mass index (BMI) \ge 35 kg/m² with obesity related complications and a diagnosis of PCOS

DURATION: 3 years

1.1 BACKGROUND

Polycystic ovarian syndrome (PCOS) affects up to 1 in 5 women and is the most common endocrine disorder in women of reproductive potential [1]. There are more than 3 million women suffering from this condition in the UK. PCOS is a heterogeneous disorder characterised by elevated circulating androgen levels, chronic anovulation, and polycystic ovaries. It manifests with hirsutism, acne, oligo or amenorrhea (i.e. few or no menstrual cycles) and subfertility. The difficulty in have children is a major cause of emotional distress. Approximately 50% of women with PCOS are overweight or obese and often have visceral adiposity when compared to age and BMI (body mass index)-matched controls [2]. PCOS complicated by obesity amplifies adverse fertility and metabolic outcomes, doubles the likelihood of developing type 2 diabetes mellitus (T2DM) and is a strong risk factor for endometrial cancer and cardiovascular disease [3]. The annual healthcare burden of PCOS in the UK, based on a conservative estimate, stands at £237 million [4]. If current trends continue without innovative prevention and treatment strategies, the annual cost is predicted to rise to £550 million by 2038.

Weight loss through any means is an effective therapy for improving subfertility in women with PCOS and obesity. Reduction in weight of 5% can help regulate the frequency of menstruation and increase the chances of a pregnancy [5]. Lifestyle modification including healthy eating and increase in physical activity is effective in causing short term weight loss, but unfortunately this is rarely maintained in the long term [6]. Strong physiological factors resist weight loss below a certain weight set point, eventually causing weight regain in more than 80% of patients and loss of any improvement in endocrine function [6]. Pharmacotherapy, including metformin and Orlistat, has a positive, but modest, impact on weight loss, and the metabolic and reproductive manifestations of PCOS [7]. Glucagon-like peptide 1 receptor agonists are more effective but have not been endorsed by NICE due to their high cost [7].

1.2 RATIONALE FOR CURRENT STUDY

In a community-based study, subfertility was reported in 72% of women with PCOS compared with 16% without [8]. Thus, a substantial proportion of women with PCOS and obesity remain sub-fertile and this has a devastating impact on their psychological health [9].

A systematic review and meta-analysis of cohort and case-control studies demonstrated that laparoscopic obesity surgery, like the vertical sleeve gastrectomy (VSG) and Roux-en-Y gastric bypass has a substantial positive impact on all of the manifestations of PCOS [10]. Obesity surgery caused weight loss of 25-30%. The incidence of PCOS preoperatively was 46% and was significantly decreased to 7% at 12-month follow-up. The incidence of pre-operative menstrual irregularity, subfertility and hirsutism were all substantially decreased at 12-month. Obesity surgery has also been shown to reduce overall mortality and the risk of developing endometrial cancer [11], T2DM [12] and cardiovascular disease [13, 14].

Modern laparoscopic obesity surgery is one of the safest operations in the field of surgery and carries similar risks of morbidity and mortality as a laparoscopic cholecystectomy [15]. Young women with PCOS rarely have significant cardiovascular or respiratory disease, making surgery even safer for this cohort. Pregnancies after obesity surgery are associated with reduced risk of gestational diabetes and excessive foetal growth, shorter gestation, but with an increased risk of small-for-gestational-age infants as compared with matched control pregnancies [16].

The knowledge gap is articulated by recent international guidelines for the assessment and management of PCOS which stated that "bariatric surgery should be considered an *experimental* therapy in women with PCOS, for the purpose of having a healthy baby, with risk to benefit ratios currently too uncertain to advocate this as fertility therapy" [17]. National and international guidelines will only change if the safety and efficacy of obesity surgery is demonstrated within randomised controlled trials (RCTs) confirming the encouraging meta-analyses of cohort studies. This proposal aims to change clinical practice and address the knowledge gap by conducting the first RCT in this field. The ultimate goal is to provide the data for an intervention that would enable women with PCOS have healthy pregnancies and children.

Hypothesis: Obesity surgery will be superior to standard medical care in increasing the number of ovulatory cycles in women with PCOS, obesity and oligo or amenorrhea.

2. STUDY OBJECTIVES

To perform a RCT comparing the safety and efficacy of obesity surgery vs. standard medical care for women with PCOS, obesity and oligo or amenorrhea.

3. STUDY DESIGN

In this prospective open-label RCT we propose to recruit 80 women with PCOS, obesity and oligo or amenorrhea from Imperial College Healthcare NHS Trust, University Hospitals Coventry & Warwickshire NHS Trust, two centres with tertiary obesity and reproductive endocrinology expertise, and the Hammersmith and Fulham GP Partnership.

They will be eligible for obesity surgery based on NICE CG189. Patients will be randomised at a ratio of 1:1, stratified by BMI and trial site to:

- Standard medical care (n=40): combination of an intensive lifestyle intervention ± pharmacotherapy or
- Obesity surgery (n=40): standard laparoscopic VSG.

3.1 STUDY OUTCOME MEASURES

Primary outcomes

• Number of ovulatory cycles within the 12 month follow-up period. Ovulation will be defined as a rise in serum progesterone ≥16 nmol/L

Secondary outcomes

Change from baseline to 12 months. For each endpoint, temporal changes, mean levels and peak levels will be analysed as appropriate:

- Number of reported menses
- Body weight
- Waist circumference
- Body composition
- Plasma lipid concentration
- Plasma liver function tests
- Plasma HbA1c
- Arterial blood pressure
- Serum LH
- Serum FSH
- Serum Oestradiol
- Serum SHBG
- Serum Testosterone
- Serum free androgen index
- Serum DHEAS
- Serum Androstenedione
- Serum AMH
- Glucose concentrations at the OGTT
- Hospital Anxiety and Depression Scale score
- Multidimensional Health Profile: Health Functioning questionnaire score
- Social Functioning Questionnaire score

- PCOS Health-Related Quality of Life score
- Modified Ferriman-Galwey hirsutism score
- Ludwig visual score
- Savin Alopecia Scale score
- Cardiff Acne Disability Index
- Number of medications
- Adverse events
- pregnancy rates

Sub-studies

- Energy expenditure
- Sleep-disordered breathing
- Endometrial clonal activity
- Adipose tissue biology
- Brain responses to food

4. PARTICIPANT ENTRY

4.1 PARTICIPANT RECRUITMENT

This will take place from:

- Outpatient clinics. The direct care team is also the research team. They will identify patients through direct clinical contact but also by looking through the databases and medical records of the obesity and reproductive clinics, and GP practices in the Hammersmith and Fulham GP Partnership.
- Online advertising via Clariness (below)
- Clariness is an international participant recruitment company for clinical trials. It advertises the trial through an online awareness campaign including search engine marketing, banner advertising on relevant websites and social media. Upon clicking an ad, these candidates will be taken through an online prescreening process. In this prescreening process patients are asked questions about their health based on the trial inclusion and exclusion criteria and those who pass this step will be referred to the investigators.

Data that the potential volunteer has provided Clariness via the ClinLife[®] website with the intention that this information will be forwarded to a participating investigator, are made available to investigators as follows: Data is stationed on a specially-equipped and accordingly-secured server on AWS in Frankfurt, Germany. (Privacy policies and security measures as stipulated by the Data Protection Act can be inserted or displayed where necessary and at any time). Data is not sent, but made available to the investigator in his/her SSL-encrypted and password-protected ClinLife[®] account. Data will only be available to sites during the enrolment period of the trial. The privacy policies and security measures according to BDSG (Bundesdatenschutzgesetz, based on the General Data Protection Regulation) apply. The appropriate trial site personnel associated with the trial will receive a neutral informative email (no personally identifiable information) requesting him/her to access his/her SSL-encrypted and password-protected ClinLife[®] account to view the patient's data. All volunteer data provided to the trial site as part of the trial registration process on ClinLife[®] will be deleted after the statutory retention period, but no later than the end of the study.

4.2 PRE-REGISTRATION EVALUATIONS

Screening will be performed to confirm that patients meet the inclusion criteria for the trial and are safe to undergo treatment for obesity following careful psychological and dietetic assessments. In addition to routine clinical care assessments, physical examination (i.e. modified Ferriman Gallwey score, Ludwig visual score and Savin Alopecia Scale) and investigations, participants will have their reproductive hormone profile checked ± pelvic ultrasonography if necessary. A urine pregnancy test will be performed. The importance of effective non-hormonal contraceptive use for the duration of the trial will be emphasized.

4.3 INCLUSION CRITERIA

- Pre-menopausal women ≥18 years old
- Body mass index (BMI) \geq 35 kg/m² with obesity related complications
- Diagnosis of PCOS based on International evidence-based guideline for the assessment and management of polycystic ovary syndrome 2018 that requires two of the following [17]:
 - i. for women > 3 years post menarche to peri-menopause: < 21 or > 35 days or < 8 cycles per year
 - ii. Hyperandrogenism
 - a. clinical hirsutism (Modified Ferriman-Galwey hirsutism score ≥ 4-6) or male pattern alopecia (positive Ludwig visual score)] or
 - b. biochemical (raised free androgen index or free testosterone)
 - iii. Polycystic ovaries on ultrasound: Using transvaginal ultrasound transducers with a frequency bandwidth that includes 8MHz, the threshold for PCOM should be on either ovary, a follicle number per ovary of > 20 and/or an ovarian volume ≥ 10ml, ensuring no corpora lutea, cysts or dominant follicles are present.

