GLM	Generalised linear model
CSR	Clinical study report
SAE	Serious Adverse Event
TEAE	Treatment emergent adverse event
AE	Adverse Event
SOC	System organs class
РТ	Preferred Term
CRF	Case Report Form

STUDY DESIGN

This is an open-label randomised-controlled clinical trial to investigate the safety and efficacy of obesity surgery vs medical care for women with polycystic ovary syndrome (PCOS), obesity and oligo- or amenorrhoea.

Patients will be randomised at a ratio of 1:1, stratified by body mass index (BMI) and trial site to:

- Medical care: a combination of lifestyle modification and pharmacotherapy or
- Obesity surgery: standard laparoscopic vertical sleeve gastrectomy (VSG).

Key Inclusion criteria

- Pre-menopausal women ≥ 18 years old
- BMI \ge 35 kg/m² with obesity-related complications
- Diagnosis of PCOS based on international evidence-based guidelines for the assessment and management of PCOS 2018

Key Exclusion criteria

- Type 1 or Type 2 diabetes mellitus
- Specific contraindications to obesity surgery
- Previous obesity surgery
- Inability to maintain adequate contraception
- Medications affecting reproductive function (e.g. oral steroids, hormonal contraceptives) at screening or 3 months previously.
- Other causes of anovulation (e.g. untreated hypothyroidism, adrenal or pituitary disorders)
- Current pregnancy or breastfeeding

Key outcomes

Reproductive

- Weekly serum progesterone
- Monthly profile of reproductive hormones
- Self-reported menses

Metabolic

- Oral glucose tolerance test measuring glucose and insulin secretion and sensitivity indices. This will take place pre-intervention, at 26 weeks and 52 weeks post-intervention.
- Monthly metabolic profile: fasting glucose, insulin, and HOMA-IR.

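### The inclusion criteria do not enforce the oligo- or amenorrhoea that defines the trial population, so women who already ovulate regularly can be randomised and dilute the effect

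*Protocol*

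**What the plan says.** **Population named.** Protocol section 3 states: "we propose to recruit 80 women with PCOS, obesity and oligo or amenorrhea". The hypothesis is that surgery is superior in "increasing the number of ovulatory cycles in women with PCOS, obesity and oligo or amenorrhea". The aim in the Study Summary, Protocol section 2, and the SAP's Study Design and section 3.1 describe the same women.

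**Population admitted.** Protocol 4.3 asks for a PCOS diagnosis "that requires two of the following": (i) irregular cycles, (ii) clinical or biochemical hyperandrogenism, (iii) polycystic ovaries on ultrasound. Option (i) is defined as "< 21 or > 35 days or < 8 cycles per year". The eligibility line of the Study Summary asks only for BMI "with obesity related complications and a diagnosis of PCOS". The SAP's key inclusion list has "Diagnosis of PCOS based on international evidence-based guidelines for the assessment and management of PCOS 2018" and no cycle requirement.

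**Endpoint and planning values.** The primary endpoint is a 12-month count of ovulatory cycles, with ovulation defined by serum progesterone of at least 16 nmol/L. Protocol section 7 and SAP section 4 plan on means of 7 (medical care) and 10 (surgery), SD 3.3, 95% power, 33 women per arm, and 40 recruited per arm.

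**The concern.** A site that follows 4.3 to the letter can randomise women whom the hypothesis does not describe. This has two consequences.

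- **Dilution.** A woman who already ovulates about once a month has little to gain on a count of ovulatory cycles, whichever arm she is in. Each such woman pulls the mean difference towards zero.
- **Labelling.** The report would state a result for women with oligo- or amenorrhoea, although eligibility did not require it. Such a woman meets 4.3, so she is not an eligibility violation under SAP 6.4 and stays in the per-protocol set as well.

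**Working it through.** **1. What the two-of-three rule admits**

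| Route | Cycle disturbance required? |
|---|---|
| (i) + (ii) | Yes, but cycles under 21 days suffice |
| (i) + (iii) | Yes, but cycles under 21 days suffice |
| (ii) + (iii) | No |

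Cycles under 21 days are neither oligo- nor amenorrhoea. Making option (i) mandatory as it stands would therefore not close the gap.

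**2. Whether anything else closes it**

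- Exclusions (Protocol 4.4) remove other causes of anovulation, not regular or ovulatory cycles.
- Screening (4.2) confirms the inclusion criteria and lists a hormone profile, but no check of cycle history.
- Online prescreening (4.1) is built on the inclusion and exclusion criteria, so it inherits the gap.
- Randomisation is stratified by BMI and site only.
- The SAP 10.1 subgroups are BMI, HOMA-IR, FAI and age. SAP 6.1 and 8.1 name no baseline cycle covariate for the primary model.

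**3. Room to gain**

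By the Protocol's own limits, a regular cycle lasts 21 to 35 days. That gives 365/35 = 10.4 to 365/21 = 17.4 cycles a year. If those cycles are ovulatory, the woman is already at or above the planned surgery mean of 10. The planned control mean of 7 lies below the Protocol's limit of 8 cycles a year.

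**4. The plan's own figure**

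Standardised difference: 3/3.3 = 0.909. Noncentrality at 33 per arm: 3/(3.3 × √(2/33)) = 3.69 on 64 degrees of freedom. Two-sided t-test power at α = 0.05 is 95.3% (94.7% at 32 per arm). The stated 33 per arm reproduces. The step to 40 is for drop-out: 33/0.85 = 39 and 33/0.80 = 42.

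**5. Dilution (illustration)**

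Assumptions not in the documents: a share f of women average m = 11 or 12 ovulatory cycles in both arms, with SD s = 1 or 3.3. The rest follow the planning values.

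- Mean difference = 3(1 − f)
- Variance in an arm with planned mean μ = (1 − f) × 10.89 + f × s² + f(1 − f)(m − μ)²
- The SD used is the square root of the average of the two arm variances.

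Example with f = 20%, m = 12, s = 1:

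- Means: 0.8 × 7 + 0.2 × 12 = 8.0 and 0.8 × 10 + 0.2 × 12 = 10.4; difference 2.4.
- Variances: 8.712 + 0.2 + 0.16 × 25 = 12.912 and 8.712 + 0.2 + 0.16 × 4 = 9.552.
- SD = √11.232 = 3.35; power at 33 per arm = 82%.

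| f | Difference | Power, SD held at 3.3 | s = 1: SD; power | s = 3.3: SD; power |
|---|---|---|---|---|
| 0 | 3.00 | 95% | – | – |
| 5% | 2.85 | 93% | 3.29-3.33; 93% | 3.36-3.40; 92% |
| 10% | 2.70 | 91% | 3.27-3.35; 90-91% | 3.41-3.49; 87-89% |
| 20% | 2.40 | 83% | 3.20-3.35; 82-85% | 3.50-3.63; 75-78% |
| 30% | 2.10 | 72% | 3.12-3.31; 72-77% | 3.56-3.73; 61-66% |

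The third column isolates dilution of the mean. With s = 1 the SD stays between 3.12 and 3.35, against 3.30, so dilution is essentially the whole loss. With s = 3.3 the SD rises and adds to it. In the worst row (30%, m = 12), dilution takes power from 95.3% to 72.1%, and the larger SD takes it on to 61.4%.

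**The case against.** Four points on the other side deserve weight.

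- **Regular bleeding is not proof of ovulation.** A reader might infer that every regular cycler has no room to improve. The documents do not support that: option (i) concerns bleeding intervals, while the endpoint rests on progesterone. Only the ovulating subset lacks headroom. The criteria do admit that subset.
- **The sample size is not shown to be wrong.** A reader might infer that it contradicts the criteria. Protocol section 7 states no baseline cycle status, and its arithmetic is right. The values 7, 10 and 3.3 come from cited sources that are not available here. If those studies already included regular cyclers, some of the dilution is already in the planning values. The firm conflict is with the hypothesis, objective and design.
- **Added variance is not the main mechanism.** It is tempting to say that such women inflate the spread. With SD 1 the average SD hardly moves; it rises clearly only if they are assumed to vary as much as everyone else.
- **The share may be small.** Section 3 names the intended population, and sites may apply it. The bleed induced before baseline (section 6) suggests that infrequent bleeding was expected. Ultrasound is done only if needed (4.2), although the (ii) + (iii) route depends on it. None of this enforces the restriction, but it makes a share of 20-30% speculative.

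It is also true that randomisation keeps the comparison valid for the women enrolled. The harm is a weaker contrast and a mislabelled population, not bias in favour of surgery.

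**Conclusion.** The inconsistency stands on the text alone, whatever the share: the stated population has oligo- or amenorrhoea, and the listed criteria do not require it. Its effect on power cannot be sized from the documents. If 5% of women are regular ovulators, the loss is 2 to 3 percentage points; at 30%, power would be 61-77%. These figures rest on the assumed share, on 11-12 ovulatory cycles in both arms with SD 1 or 3.3, and on no treatment effect in these women. They are t-test powers, in line with the plan's own calculation, whereas SAP 8.1 makes a Poisson model primary. The documents do not show that any such woman has been enrolled.

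**What to change.** Reconcile Protocol 4.3, the eligibility line of the Study Summary and the SAP key criteria with the hypothesis, objective and design. Make oligo- or amenorrhoea mandatory, using the Protocol's own limits (cycles over 35 days or fewer than 8 a year, amenorrhoea included), plus at least one of (ii) and (iii). Record cycle history at screening so that the criterion can be audited.

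If women without oligo- or amenorrhoea are already randomised:

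- keep them in the ITT set;
- report pre-trial cycle status by arm;
- prespecify, before database lock, an analysis restricted to women with oligo- or amenorrhoea;
- adjust the primary model for pre-trial cycle frequency, taken from history because the bleed before baseline is induced.

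The cost is a protocol amendment needing ethics approval, a matching SAP edit, and a slightly smaller recruitment pool. If recruitment is well advanced, only the analysis steps will help.

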4.4 EXCLUSION CRITERIA

- Type 1 or Type 2 diabetes mellitus
- Specific contraindications to obesity surgery
- Previous obesity surgery
- Inability to maintain adequate contraception
- Medications affecting reproductive function (e.g. oral steroids, hormonal contraceptives) at screening or 3 months previously.
- Other causes of anovulation (e.g. untreated hypothyroidism, adrenal or pituitary disorders)
- Current pregnancy or breastfeeding
- History of any medical, psychological or other condition, or use of any medications, including overthe-counter products, which, in the opinion of the investigators, would either interfere with the study or potentially cause harm to the volunteer.
- Without access at home to a telephone or other factor likely to interfere with ability to participate reliably in the study.

4.5 WITHDRAWAL CRITERIA

All participants are free to withdraw at any time from the protocol treatment without giving reasons and without prejudicing further treatment. Should they wish to withdraw their consent, all of their data to date will be held.

5. ADVERSE EVENTS

5.1 DEFINITIONS

Adverse Event (AE): any untoward medical occurrence in a patient or clinical study subject.

Serious Adverse Event (SAE): any untoward and unexpected medical occurrence or effect that:

- Results in death
- Is life-threatening refers to an event in which the subject was at risk of death at the time of the event; it does not refer to an event which hypothetically might have caused death if it were more severe
- Requires hospitalisation, or prolongation of existing inpatients' hospitalisation
- Results in persistent or significant disability or incapacity
- Is a congenital anomaly or birth defect

Medical judgement should be exercised in deciding whether an AE is serious in other situations. Important AEs that are not immediately life-threatening or do not result in death or hospitalisation but may jeopardise the subject or may require intervention to prevent one of the other outcomes listed in the definition above, should also be considered serious.

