5.2.1 Non serious AEs

All such events, whether expected or not, should be recorded.

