5.2.2 Serious AEs

An SAE form should be completed and faxed to the Chief Investigator within 24 hours. However, relapse and death due to causes unrelated to the trial interventions, and hospitalisations for elective treatment of a pre-existing condition do not need reporting as SAEs.

All SAEs should be reported to the London-Dulwich Research Ethics Committee where in the opinion of the Chief Investigator, the event was:

- 'related', ie resulted from the administration of any of the research procedures; and
- 'unexpected', ie an event that is not listed in the protocol as an expected occurrence

Reports of related and unexpected SAEs should be submitted within 15 days of the Chief Investigator becoming aware of the event, using the NRES SAE form for non-IMP studies. The Chief Investigator must also notify the Sponsor of all SAEs.

Local investigators should report any SAEs as required by their Local Research Ethics Committee, Sponsor and/or Research & Development Office.

Pregnancy

We ask participants to use non-hormonal contraception for the duration of the study. This is especially important for those in the surgical arm as pregnancy in the first 12 months following obesity surgery should be avoided due to the risk of nutritional deficiencies and other potential complications.

Contact details for reporting SAEs

[contact] [name] [contact], attention [name] Please send SAE forms to: Department of Investigative Medicine Imperial College London [name] [contact] (Mon to Fri 09.00 – 17.00)

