9 SAFETY ANALYSES

9.1 PRIMARY SAFETY OUTCOME

The primary safety outcome will be the incidence risk of treatment-emergent serious adverse events (SAEs) through the 52-week follow-up period. We will evaluate this outcome via a Fisher's exact test. Results will be presented as numbers of patients with the event (percentage).

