9.3.4 Deaths

If a death occurs during the trial, relevant information (including study day of death relative to index initiation, cause of death, and adverse event leading to death) will be supplied in a data listing.

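### Protocol 5.1 makes unexpectedness part of the SAE definition, in conflict with 5.2.2, and may thereby keep recognised serious surgical complications out of the primary safety outcome

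*Protocol*

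**What the plan says.** Protocol 5.1 defines an adverse event (AE) as "any untoward medical occurrence in a patient or clinical study subject", with no condition on expectedness. The SAE definition that follows adds one: an SAE is "any untoward and unexpected medical occurrence or effect that" meets one of the listed seriousness criteria. A closing clause allows medical judgement for other important AEs, which if they "may jeopardise the subject or may require intervention to prevent one of the other outcomes listed in the definition above, should also be considered serious".

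Protocol 5.2.1 says of non-serious AEs: "All such events, whether expected or not, should be recorded".

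Protocol 5.2.2 requires an SAE form within 24 hours and notification of the Sponsor for all SAEs. SAEs go to the ethics committee only if they are related and also "unexpected', ie an event that is not listed in the protocol as an expected occurrence". The same section exempts from SAE reporting "relapse and death due to causes unrelated to the trial interventions", and elective admissions for pre-existing conditions.

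SAP 9.1 states: "The primary safety outcome will be the incidence risk of treatment-emergent serious adverse events (SAEs) through the 52-week follow-up period". The test is Fisher's exact test. The SAP contains no SAE definition of its own. SAP 9.3 also compares any treatment-emergent adverse event (TEAE) and counts by Clavien-Dindo grade. SAP 9.3.4 provides a listing: "If a death occurs during the trial, relevant information" is to be given.

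**The concern.** Seriousness describes the outcome of an event. Expectedness describes whether it was foreseen. The first should decide what is counted as serious harm; the second normally decides only what is sent on for expedited review. Protocol 5.1 merges the two, and SAP 9.1 inherits the result.

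Recognised procedural complications arise mainly in the arm that has a procedure. Excluding foreseen events would therefore not act evenly on the two arms. Safety stands beside efficacy in the objective (Protocol 2, SAP 3.1), and Protocol 1.2 gives uncertainty about risk and benefit as the reason for the trial. The main safety comparison should not depend on how each site reads one word, least of all in an open-label trial.

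**Working it through.** **1. The definitions side by side**

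| Place | Is expectedness a condition? |
|---|---|
| Protocol 5.1, AE | No |
| Protocol 5.1, SAE | Yes |
| Protocol 5.2.1, non-serious AEs | No; recorded either way |
| Protocol 5.2.2, 24-hour form and Sponsor | Not stated, but inherited from the SAE definition |
| Protocol 5.2.2, ethics committee | Yes, as a filter on SAEs |
| SAP 9.1, primary safety outcome | Not stated, but inherited |
| SAP 9.3.1, TEAE | No; timing or worsening only |

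The ethics committee filter has a purpose only if some SAEs can be expected. Protocol 5.1 says none can. The two sections do not agree.

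**2. Two readings of the word**

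- *The meaning in 5.2.2.* An event is expected only if the protocol lists it. The text provided contains no such list, so nothing is expected and no complication drops out.
- *The ordinary meaning.* A known complication of sleeve gastrectomy that causes readmission is foreseen, so it is not an SAE under 5.1.

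Protocol 5.1 does not refer to the meaning in 5.2.2, so either reading is open to an investigator.

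**3. Does the judgement clause repair this?** Only in part. It is written for AEs that are not immediately life-threatening or do not lead to death or hospitalisation. A foreseen complication that causes admission or threatens life falls outside it. Taken literally, a milder foreseen event can be upgraded to serious and a worse one cannot.

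**4. Size, on assumed rates**

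Inputs from the documents: 40 women per arm (Protocol 7, SAP 4), Fisher's exact test (SAP 9.1), two-sided 0.05 (SAP 6.1). The 40 rests on the efficacy endpoint. The normal approximation, 2 × (1.960 + 1.645)² × 3.3² / 3² = 31.4, gives 32 per group, and the t-test version gives the stated 33. There is no safety power figure to reproduce. I assume all 40 per arm enter the safety population.

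Let p be the true SAE risk in the surgery arm, q that in the medical arm, and f the share of surgical patients with an SAE who drop out of the count, with none dropped in the medical arm. Then

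counted risk difference = p(1 − f) − q, and bias = −f × p.

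For assumed p = 10% and q = 2.5%:

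| f | Expected patients, surgery v medical | Risk difference (points) |
|---|---|---|
| 0 | 4.0 v 1.0 | +7.5 |
| 0.5 | 2.0 v 1.0 | +2.5 |
| 0.75 | 1.0 v 1.0 | 0 |
| 1 | 0.0 v 1.0 | −2.5 |

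Over p from 5% to 20% and f from 0.25 to 1, the bias runs from −0.25 × 5 = −1.25 to −1 × 20 = −20 points. At f = 0 there is none.

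**5. Effect on the test**

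Fisher's test at 40 v 40 gives p = 0.49 for 2 v 0, 0.12 for 4 v 0, 0.055 for 5 v 0 and 0.026 for 6 v 0. At least 6 v 0 is needed. The chance of a significant surgical excess, by exact enumeration:

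| Assumed risks | f = 0 | f = 0.25 | f = 0.5 |
|---|---|---|---|
| 20% v 2.5% | 60% | 32% | 9% |
| 10% v 2.5% | 9% | 3% | 0.5% |

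**The case against.** The strongest reply is that the protocol explains the word once, in 5.2.2, and on that explanation nothing is expected because nothing is listed. The stated intention to notify the Sponsor of all SAEs, and the later filter for the ethics committee, also suggest that the authors did not mean to exclude foreseen events. This stands as far as it goes: exclusion is possible, not shown. It does not settle the matter, because 5.1 does not adopt that explanation and a site without a list must fall back on judgement.

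The second reply is that the data survive. All AEs are to be reported (Protocol 5.2), and the TEAE and Clavien-Dindo comparisons ignore expectedness. This also stands. It confines the problem to SAE-based results: the primary test, the serious TEAE summaries in SAP 9.3.3 and the seriousness flag in the SAP 9.3.1 listing. Reanalysis cannot, however, restore a 24-hour form or a Sponsor notification that was never made.

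A reader might go further and infer three things that the documents do not support.

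- *That the comparison is already biased.* This depends on which reading the sites use.
- *That losing one event would reverse the result of the test.* If 2.5% to 10% of 40 surgical patients have a recognised serious complication, that is 1 to 4 patients. Even 4 v 0 is not significant, so those events alone do not change the outcome whether counted or not. A reversal needs at least 6 surgical patients with an SAE against none, or 6/40 = 15%.
- *That the exemption for unrelated deaths adds to a bias towards surgery.* Its wording applies to both arms, deaths are listed under SAP 9.3.4, and death is tabulated as a reason for discontinuation under SAP 6.2. What is missing is only a statement that such deaths count in SAP 9.1.

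**Conclusion.** The definition is wrong as written, and this much is certain: 5.1 conflicts with 5.2.2, and the primary safety outcome inherits the conflict. The consequence is conditional. If the word is read in its ordinary sense, recognised serious complications may be left out of the SAE count and of SAE reporting, and this would probably favour the surgery arm.

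The direction rests on the assumption that such complications arise mainly after surgery. The size rests wholly on assumed rates. At those rates the main damage is to the estimated risk difference and to timely reporting; the effect on the significance test is material only if surgical SAE risk is well above 10%.

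**What to change.** 1. **Protocol 5.1:** delete the words that require an SAE to be unexpected, so that an SAE is any untoward occurrence that meets a seriousness criterion.
2. **Protocol 5.2.2:** keep expectedness and relatedness only as the filter for ethics committee reporting, and add a reference list of expected events for that purpose. It follows that an unrelated death is still reported as an SAE and is only held back from the ethics committee route.
3. **SAP 9.1:** state that SAEs, including all deaths, are counted by the seriousness criteria alone, whatever their expectedness or relatedness.
4. **Before database lock:** re-screen all recorded AEs against those criteria and correct the seriousness flag where needed.

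The cost is a wording amendment, a check of the AEs already recorded and slightly more SAE forms. Sample size, visits and the planned test do not change.
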